6.1.3 Inclusion criteria

- Age 0 years to 25 years (upper age limit can change in future based on data availability)
 Case recruitment is prioritised to the following:
 - a clinical or genetic diagnosis of FH (excluding confirmed homozygous, compound heterozygous/digenic FH)
 - age 7 years or older with a baseline cholesterol measurement (ideally at diagnosis) and planned clinical follow-up [based on current NICE guidelines for starting LLT by age 10, these children will have the opportunity to start LLT over the study duration]
 - o at least 1 available LDL-C measurement before age 16 years
 - o for cases on LLT, date treatment started and the pre-treatment LDL-C measurement
- Ability of participant with FH to provide informed consent at age 16 years or older
- Ability of participant's parent/guardian to provide informed consent for participants with FH under age 16 years
- Ability of participant with FH to provide informed assent at age 5-15 years for clinical data collection
- Attending a clinical site for their FH that has been approved for study recruitment

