Clinical data collection will use REDCap (Research Electronic Data Capture https://www.projectredcap.org/), a secure web application, for the PFHR electronic database accessible by studyapproved clinicians who see individuals diagnosed with FH in childhood and adolescence. Clinicians (or a nominated staff member) will be 1) approved for recruiting, consenting, and registering patients for clinical data collection, 2) provided with a username and password for entry of clinical data at registration and clinical follow-ups.

Site-specific monthly data monitoring will be conducted. Monthly targets for cohort recruitment at key clinical sites will consist of current paediatric FH patients being seen in these sites who are not yet registered on the PFHR (recruitment with retrospective longitudinal data entry and prospective follow-

up) and newly presenting paediatric FH cases (prospective recruitment and follow-up). An **Internal Pilot**, starting month 8 of the project, will be carried out over the first year of recruitment with monthly monitoring of recruitment data on total case numbers, data completeness on cholesterol and LLT, and representativeness of ethnic diversity.

In recognition of the need to ensure robust information on the clinical management of FH and the use of LLT including benefits and risks from both clinical practitioner and patient perspectives, **two new elements will be added to the PFHR: patient questionnaires and interviews**. Patients who consent to PFHR clinical data collection can additionally express an interested in being contacted for involvement in further research. Those patients who agree to being contacted for further research will be invited to participate in **questionnaire data collection (4 repeated questionnaires per participant at baseline, 8, 16, 24 months) and/or semi-structured interview data collection**.

Questionnaires will capture greater detail and a direct patient-reported indication of changes in LLT adherence and side-effects/intolerance over time as well as healthcare utilisation experience. To measure changes in adherence over time, the Medication Adherence Report Scale,²⁷ a previously validated tool, will be used within the questionnaire at each timepoint.

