6.1.2 Eligibility criteria for the Register

Individuals who have been diagnosed with FH before the age of 18 years and have been seen and followed-up in an NHS clinical setting for management of their FH during childhood (i.e., under age 18) are eligible for clinical data collection. Individuals with FH who are age 16 years or older and parents/guardians of individuals with FH who are under age 16 are eligible for questionnaire and interview data collection.

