LDL-C changes in those exposed to LLT will be compared with changes in those never exposed or unexposed up to a certain age, measured as the difference between the earliest and later follow-ups. We will use inverse probability of treatment weighting techniques^{28,29} to balance exposed and unexposed groups according to both baseline and time-varying measured confounders: family history of CVD and/or FH in family, gender, genetic testing, body mass index (BMI), ethnicity, other health conditions, reasons for not being on LLT or non-adherence, process factors such as attendance frequency, and socioeconomic deprivation (using post-code linkage to index of multiple deprivation).

We will primarily estimate intention-to-treat effects, i.e. the effect of prescribing LLT to children with FH on LDL-C levels.³⁰ We will then estimate per-protocol effects, which corresponds to the effect of continuously taking LLT during the following period. Potential treatment non-adherence and loss to follow-up will be accounted for via censoring weights.³⁰ Missing data in both the LDL-C outcomes and confounders will be addressed using multiple imputation.

We will conduct sensitivity analyses to assess the extent to which the effects of age and LDL-C at initiation are robust to potential unmeasured confounding. We will adopt the E-value approach,³¹ which essentially explores how strong (association with both LLT initiation and LDL-C outcomes) the unmeasured confounders need to be to change the study conclusions. These analyses will be informed by discussions with clinical specialists and PPIE groups, and the HCP questionnaire.

This will be a descriptive analysis with the ultimate aim to derive effectiveness estimates that will feed into the cost-effectiveness model, where uncertainty will be fully propagated.³² However, initial assessment, based on pre- and post-puberty in current PFHR data shows children initiating LLT before age 12 years achieved a mean reduction in LDL-C of 2.199 after initial mean levels of 6.115 (pooled SD=2.51) and those initiating LLT at 12 or older achieved a mean reduction in LDL-C of 1.748 after initial mean levels of 5.570 (pooled SD=1.53). Demonstrating this difference at 90% power and 0.05 significance level with a 60-40 allocation ratio (as in the current Register) would require 560 children initiating LLT before age 12 and 376 initiating LLT at 12 or older, which is within our planned recruitment target.

Secondary analyses:

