- Age 0 years to 25 years (upper age limit can change in future based on data availability)
 - Within the first 4 years of recruitment, case recruitment is prioritised to:
 - a clinical or genetic diagnosis of familial hypercholesterolaemia (excluding confirmed homozygous, compound heterozygous/digenic FH)
 - age 7 years or older with a baseline cholesterol measurement (ideally at diagnosis) and planned clinical follow-up
 - o at least 1 available LDL-C measurement before age 16 years
 - for cases on LLT, date treatment started and the pre-treatment LDL-C measurement

The above prioritised inclusion criteria are to ensure the primary study objective aligned with the NIHR HTA award (NIHR134993) is answerable, which assesses the clinical effectiveness of cholesterol-reducing mediations which are typically not started until age 8 onwards. Permission to recruit prospective patients who do not meet the prioritised inclusion criteria must be approved by the Study Leads.

- Ability of participant with FH to provide informed consent at age 16 years or older
- Ability of participant's parent/guardian to provide informed consent for participants with FH under age 16 years
- Ability of participant with FH to provide informed assent at age 5-15 years for clinical data collection
- Attending a clinical site for their FH that has been approved for study recruitment

Exclusion criteria

None beyond limits of eligibility and inclusion criteria other than the following language restrictions:

 To facilitate completion by non-English speaking children/young people and/or parents/guardians, study materials can be translated into the 4 commonest non-English

Page 17 of 37

Paediatric FH Register Study Protocol IRAS ID: 324246 18 June 2024 Final version 2.0

languages in the UK and telephone support for patient information sheets and completion of completion of consent forms and questionnaires will be available through LanguageLine UK. However, this may still result in some language restrictions which could exclude some potential participants.

 Availability of interpreters will be assessed on an as needed basis for interviews. However, inability to complete interview in English or in a language with an available interpreter will exclude some potential participants.

Expected duration of participant participation

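### New Register entrants must still be attending clinic, so children who stopped LLT and left care before enrolment have no record; this may bias the age-at-initiation contrast, and the censoring weights cannot correct it

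*Protocol*

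**What the plan says.** Section 6.1.2 sets a wide frame: diagnosis before age 18, and patients who "have been seen and followed-up in an NHS clinical setting for management of their FH during childhood". Section 6.1.3 narrows it in two ways.

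- One bullet is unconditional: "Attending a clinical site for their FH that has been approved for study recruitment".
- A second group of criteria is introduced by "Case recruitment is prioritised to the following" and includes "age 7 years or older with a baseline cholesterol measurement (ideally at diagnosis) and planned clinical follow-up". These are priorities. The Appendix (Inclusion criteria) allows exceptions: "Permission to recruit prospective patients who do not meet the prioritised inclusion criteria must be approved by the Study Leads".

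Section 6.1.1 gives the source of the retrospective data as "current paediatric FH patients being seen in these sites who are not yet registered on the PFHR (recruitment with retrospective longitudinal data entry", together with newly presenting cases followed prospectively. The Appendix (Strategies for recruitment and retention) limits reminders and re-invitations to patients still under the site's care. Its Study Data section sets site targets of at least 60% of cases with 3 or more years of follow-up, which may be retrospective, and at least 30% with prospective data. Section 10 plans the main Register analysis on retrospective and prospective data together.

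Section 7.1(a) aims first at an intention-to-treat effect of prescribing LLT. On attrition it states: "Potential treatment non-adherence and loss to follow-up will be accounted for via censoring weights". Section 7.6 treats the effect of adherence on LDL-C reduction as already contained in the Register and CPRD estimates.

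**The concern.** An intention-to-treat effect of prescribing LLT needs everyone who was prescribed it, including those who later stopped and left the clinic. For new recruits with old notes, entry depends on something that happened after LLT start, namely still being in care at recruitment. Those who stopped and left are not lost to follow-up in the analytic sense, because they were never in the data. Weights built on registered children, whether for censoring, attendance frequency or non-adherence, cannot stand in for them.

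The length of this selection differs between the groups being compared. Of two 15-year-olds recruited on the same day, one who started at 9 had to remain in care for 6 years and one who started at 14 for 1 year. If stoppers leave faster than continuers, the first group has been more strongly filtered towards continuers. Age at initiation is the study's core question, and the estimate feeds the economic model. If stoppers are missing, the Section 7.6 premise that adherence is built into the LDL-C estimates is not met for this part of the sample.

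**Working it through.** **1. The planning difference.** Section 7.1(a) gives mean reductions of 2.199 (SD 2.51) for LLT start before 12 and 1.748 (SD 1.53) for start at 12 or older. The difference is 2.199 − 1.748 = 0.451 mmol/L. With SD = √((2.51² + 1.53²)/2) = 2.079, two-sided 5% (sidedness is not stated), 90% power and 60:40 allocation, the requirement is 558 and 372. The plan states 560 and 376, so its figure reproduces. The point here does not depend on it; 0.451 serves only as a yardstick.

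**2. How much follow-up may predate enrolment.** A site can meet its prospective-data target with up to 100% − 30% = 70% of cases lacking prospective data. New recruits number 1,374 − 613 = 761, which is 761/1,374 = 55% of the target Register.

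**3. Illustration of size.** The documents give no rates of leaving care, so these are assumptions: a share s = 0.25 of initiators stop; the reduction is 2.2 mmol/L in continuers and 0 in stoppers; the yearly rate of leaving clinic is hs = 0.15 for stoppers and hc = 0.05 for continuers. The true mean is 2.2 × 0.75 = 1.65 in both age groups. Among those still attending after y years:

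stopper share = s·exp(−hs·y) / [s·exp(−hs·y) + (1 − s)·exp(−hc·y)], and observed reduction = 2.2 × (1 − stopper share).

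| y (years) | stopper share | observed reduction (mmol/L) |
|---|---|---|
| 1 | 23.2% | 1.69 |
| 2 | 21.4% | 1.73 |
| 4 | 18.3% | 1.80 |
| 6 | 15.5% | 1.86 |

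- 6 versus 1 year: 1.86 − 1.69 = 0.17 mmol/L, or 38% of 0.451.
- 4 versus 2 years: 1.80 − 1.73 = 0.07 mmol/L, or 15% of 0.451.
- At 6 versus 1, varying s over 15–35% and hs over 0.10–0.25 gives 0.06 to 0.37 mmol/L.

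**4. Dilution by earlier registrations.** If the 613 patients registered by 2019 carried none of this selection (an assumption), the figures shrink by 761/1,374: 0.17 × 0.55 ≈ 0.09 and 0.07 × 0.55 ≈ 0.04 mmol/L.

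**5. Different assumptions, and direction.** A second model lets children stop gradually, with a reduction of 2.199 on LLT and 0 after stopping.

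- Early starters 6 years and late starters 2 years from initiation, stopping 3–16% per year, stoppers leaving at 10–30% per year and continuers at 3–5%: net bias towards early start of 0.05 to 0.32 mmol/L.
- Stoppers leaving at the same rate as continuers: 0.
- Late starters (3 years from initiation) stopping at 15–25% and then leaving at 30–50% per year, early starters (6 years) at 3–5% and 10%, continuers leaving at 3%: −0.11 to −0.30 mmol/L, that is, against early start.

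For scale, Section 5.1 cites adherence as low as 20% at about 10 years. At a constant rate that is −ln(0.2)/10 = 0.16 per year, the upper end of the stopping range used.

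**The case against.** **Planned follow-up is not compulsory.** A reader might infer that children enter only if further follow-up is planned. The text does not support this: it is a priority that the Study Leads can set aside. Attendance is the binding rule, and even that is applied with some tolerance, since re-invitations run for up to two years and allow for missed appointments. This stands, and the point rests on attendance.

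**The direction is not established.** A reader might infer that the design flatters early initiation. The documents give no departure rates by starting age. Selection works through time since initiation at enrolment, not starting age as such, and Section 5.1 notes barriers to continuing LLT across the transitions into adolescence and adulthood. Step 5 shows that the bias can vanish or reverse. This also stands.

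**The size depends on the contrast chosen.** Mean follow-up in the existing Register is 2.9 years (SD 1.8), so 6 years is well out in the tail. Assigning stoppers no reduction throughout also ignores their measurements while on LLT. The 0.17 should be read as the upper of two illustrative values, not as an estimate.

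**CPRD is a counterweight.** Section 7.1 repeats the LDL-C analysis in CPRD, which does not depend on specialist clinic attendance. Section 7.6 takes persistence to age 18 from CPRD and names CPRD effects as a scenario. It is only a partial check: Section 6.2 says it has no specialist lipid clinic records and less confounder information than the Register, and its feasibility work found a mean of 3 LDL-C measures.

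**Stoppers who still attend are not excluded.** The data requirement for cases on LLT might be read as shutting them out. It does not say so, and reasons for not being on LLT are collected and used.

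**A supporting analysis may belong in the SAP.** That is fair, and its absence from the protocol is not itself the fault. The entry rule, the intention-to-treat aim and the reliance on censoring weights are all fixed in the protocol, and together they leave the gap.

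**Conclusion.** The concern holds in limited form. For new recruits with retrospective notes, children who stopped LLT and left care before enrolment are absent by design, and the planned weights cannot restore them. The stated intention-to-treat effect is therefore not delivered for that part of the sample. The age-at-initiation contrast may be biased, plausibly in favour of early start.

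Under the illustrative rates the spurious difference is about 0.07 to 0.17 mmol/L against 0.451, and about 0.04 to 0.09 once diluted by the earlier registrations. All of this depends on stoppers leaving care faster than continuers, which the documents neither state nor rule out. They do not support a claim that the result will favour early start, or any single figure for the bias. This is a cheap improvement, not a flaw that invalidates the study.

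**What to change.** 1. In Section 7.1(a), add a supporting analysis limited to children registered before, or within 12 months after, LLT start. Report it beside the main age-at-initiation estimate, and carry it into the economic model as a scenario alongside the CPRD one.
2. In Section 7.2, for Register side-effect and adverse-event incidence rates, add a sensitivity analysis that counts person-time and events from registration (delayed entry).
3. State in Section 7.1 that the estimate pooling retrospective and prospective data applies to children retained in care.

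No new data collection is needed for new recruits: consent forms are dated, and LLT start date is a prioritised data item. I assume registration dates are also held for the 613 earlier patients. The cost is a smaller sample and wider intervals in the supporting analyses. The documents do not allow the remaining number to be calculated. A 12-month window shortens the selection but does not remove it entirely.

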6.1.4 Exclusion criteria

None beyond limits of eligibility and inclusion criteria other than the following language restrictions:

 To facilitate completion by non-English speaking CYP and/or parents/guardians, study materials can be translated into the 4 commonest non-English languages in the UK and telephone support for patient information sheets and completion of completion of consent forms and questionnaires will be available through LanguageLine UK. However, this may still result in some language restrictions which could exclude some potential participants.

6.1.5 Recruitment and consent procedure

Patients are recruited for clinical data collection by clinicians (or a nominated staff member who will usually be a clinical member of staff with experience of working with the patient group) at NHS clinical sites seeing individuals diagnosed with FH during childhood across England and Wales. The clinician or nominee will inform the participant and/or their parent/guardian, of all aspects pertaining to participation in the study. The clinical setting is chosen for base recruitment as data collection is from clinical records and consultations with health professionals. Patients or their parents/guardians are initially approached for recruitment during or between clinic visits, via email, telephone, text message or post, based on accepted recruitment practices and patient-contact methods within the clinical site. Clinical teams also have the option of using trained NHS research volunteers who will be approved by the site PI to assist in recruiting participants. The research volunteers will have lived experience of FH in their family or undergo training paediatric FH. It is possible for patients or parents/guardians to approach their clinicians with interest in participating in the study; their clinical team will need to have been approved for data collection prior to recruitment.

Patients aged 16 years and over or parents/guardians of younger patients are recruited for questionnaire data collection if they express an interest in being contacted for participation in further research when they enrol for clinical data collection. The study team at the University of Nottingham will directly contact individuals who express an interest in further research to invite them to participate in questionnaire data collection.

Patients aged 16 years and over or parents/guardians of younger patients are recruited for semi-structured interviews if they express an interest in being contacted for participation in further research when they enrol for clinical data collection and based on a sampling framework that uses clinical and questionnaire data to obtain diversity based on sociodemographic, geographical, and FH-related characteristics (adherence, side-effects, healthcare service use). Participants with FH aged 16 years or over will have the choice to be interviewed alone or with their parent/guardian. Parents/guardians will have the choice to be interviewed alone or with their child who has FH (i.e., child on the clinical Register), if the child is age 11-15 years.

Informed consent for clinical data collection will be obtained as follows:

- Informed consent by the individual with FH if they are age 16 years or older
- Informed consent by a parent/guardian if the individual with FH is under age 16 years
- Informed assent by the individual with FH if they are under age 16 years (in conjunction with parent/guardian consent)
- Informed consent by the individual with FH who has previously provided informed assent when they reach 16 years of age

Informed consent for questionnaire data collection will be obtained as follows:

- Informed consent by the individual with FH if they are age 16 years or older
- Informed consent by a parent/guardian if the individual with FH is under age 16 years

Informed consent for semi-structured interviews will be obtained as follows:

- Informed consent by the individual with FH if they are age 16 years or older
- Informed consent by a parent/guardian if they participate in an interview with their child with FH who is age 16 years or older (in conjunction with their child's consent)
- Informed consent by a parent/guardian if the individual with FH is under age 16 years
- Informed assent by the individual with FH if they are age 11-15 years and participate in an interview with their parent/guardian (in conjunction with parent/guardian consent)

Participant information sheets, consent forms and assent forms are in paper or electronic format. Electronic format will be via the REDCap secure web application. Where individuals require languages other than English, paper copies will be available in the next 4 commonest languages in the UK.

Should there be any amendments to the final protocol that might affect a participant's participation in the study, continuing consent/assent will be obtained using amended consent/assent forms which will be signed by the participant.

